## **6** ANALYSIS

### 6.1 Primary outcome

### 6.1.1 IgE-mediated egg and/or peanut allergy at 12 months of age

Binary outcome based on measurements on the infant at 12 months of age. IgE-mediated egg and/or peanut allergy is defined as an allergic reaction to egg with sensitisation to egg and/or an allergic reaction to peanut with sensitisation to peanut. Sensitisation is defined as a 3mm or greater weal size based on a skin prick test (SPT). Infants with a positive SPT who do not proceed with the corresponding food challenge due to previous anaphylaxis or allergic reaction will be considered positive for IgE-mediated egg and/or peanut allergy; otherwise, the allergic reaction will be established according to an oral food challenge.

Note: Sensitisation is defined the same way throughout Section 6.2.

### 6.2 Secondary clinical outcomes

### 6.2.1 Sensitisation to egg

Binary outcome based on a positive SPT to egg.

#### 6.2.2 Sensitisation to peanut

Binary outcome based on a positive SPT to peanut.

### 6.2.3 IgE-mediated egg allergy

Binary outcome based on an allergic reaction to egg with sensitisation to egg. Infants with a positive SPT for egg who do not proceed with the egg food challenge due to previous anaphylaxis or allergic reaction to egg will be considered positive for IgE-mediated egg allergy; otherwise, the allergic reaction will be established according to an oral egg challenge.

#### Statistical Analysis Plan

Page 14

#### 6.2.4 IgE-mediated peanut allergy

Binary outcome based on an allergic reaction to peanut with sensitisation to peanut. Infants with a positive SPT for peanut who do not proceed with the peanut food challenge due to previous anaphylaxis or allergic reaction to peanut will be considered positive for IgE-mediated peanut allergy; otherwise, the allergic reaction will be established according to an oral peanut challenge.

#### 6.2.5 Infant eczema

Binary outcomes based on a medical diagnosis of infant eczema by 4 and 12 months of age.

## 6.3 Exploratory laboratory outcomes

#### 6.3.1 Maternal egg specific IgG4 concentrations

Continuous outcomes based on egg specific IgG4 levels (mgA/L) in maternal blood samples at 34-38 weeks gestation and 4 months postnatal age (Perth and Sydney women only). Egg-specific IgG4 serum antibody concentrations will be measured using the ImmunoCAP 250 system, which has a lower limit of detection of 0.07 mgA/L.

#### 6.3.2 Maternal peanut specific IgG4 concentrations

Continuous outcomes based on peanut specific IgG4 levels (mgA/L) in maternal blood samples at 34-38 weeks gestation and 4 months postnatal age (Perth and Sydney women only). Peanut-specific IgG4 serum antibody concentrations will be measured using the ImmunoCAP 250 system, which has a lower limit of detection of 0.07 mgA/L.

### 6.3.3 Infant egg specific IgG4 concentrations

Continuous outcomes based on egg specific IgG4 levels (mgA/L) in infant blood samples at 4 and 12 months of age (Perth and Sydney infants only). Egg-specific IgG4 serum antibody concentrations will be measured using the ImmunoCAP 250 system, which has a lower limit of detection of 0.07 mgA/L.

### 6.3.4 Infant peanut specific IgG4 concentrations

Continuous outcomes based on peanut specific IgG4 levels (mgA/L) in infant blood samples at 4 and 12 months of age (Perth and Sydney infants only). Peanut-specific IgG4 serum antibody concentrations will be measured using the ImmunoCAP 250 system, which has a lower limit of detection of 0.07 mgA/L.

Version 1.0

Statistical Analysis Plan

Page 15

### 6.3.5 Infant egg specific IgE concentrations

Continuous outcomes based on egg specific IgE levels (kUA/L) in infant blood samples at 4 and 12 months of age (Perth and Sydney infants only). Egg-specific IgE serum antibody concentrations will be measured using the ImmunoCAP 250 system, which has a lower limit of detection of 0.1 kUA/L.

### 6.3.6 Infant peanut specific IgE concentrations

Continuous outcomes based on peanut specific IgE levels (kUA/L) in infant blood samples at 4 and 12 months of age (Perth and Sydney infants only). Peanut-specific IgE serum antibody concentrations will be measured using the ImmunoCAP 250 system, which has a lower limit of detection of 0.1 kUA/L.

## 6.4 Analysis methods

### 6.4.1 Overall analysis approach

The primary outcome and all secondary clinical outcomes (see Sections 6.1 and 6.2) will be analysed using log binomial regression models, with the effect of treatment described as a relative risk with a 95% confidence interval. Should any of the models fail to converge, a known problem with log binomial regression, a log Poisson model using generalised estimating equations (independence working correlation structure assumed) will be used for analysis (2). If the number of infants experiencing an outcome is considered too small for a regression model to be sensible (less than 5 events in either randomised group), then, regardless of convergence, a Fisher exact test will be performed instead.

To account for censoring due to the lower detection limits of the measuring equipment, the exploratory laboratory outcomes (Section 6.3) will be analysed using tobit regression models. Based on previous experience with these measures (3), the IgG4 and IgE concentrations will be log transformed prior to analysis to satisfy an assumption of homogeneous error variance. The effect of treatment on the latent (uncensored) IgG4 and IgE concentrations will be described as a ratio of means with a 95% confidence interval. Should the assumption of homogeneous error variance on the log scale be deemed unreasonable, based on a scatterplot of model residuals versus fitted values, other transformations will be explored and justified as appropriate.

### 6.4.2 Covariate adjustment

Given recommendations to adjust for variables used to stratify the randomisation when estimating treatment effects (4), analyses will be adjusted for city (Adelaide, Melbourne, Perth, Sydney) and

Version 1.0

#### PrEggNut Study Statistical Analysis Plan

#### Page 16

birth order (first or subsequent born child to the mother). Adjustment will also be made for infant sex and maternal history of allergic disease (defined as a medical diagnosis of asthma, eczema, hayfever or food allergy), both considered important prognostic variables for infant allergic disease outcomes (5, 6). All adjustment variables will be treated as fixed effects in the analysis models. For each outcome, both unadjusted and adjusted analyses will be performed, with the adjusted analyses used to draw final conclusions about the effect of treatment.

If adjusted models fail to converge for any of the outcomes, adjustment variables will be removed sequentially (infant sex, then maternal history of allergic disease, then city, then birth order) until convergence is achieved. Adjusted analyses will not be considered for binary outcomes analysed using a Fisher exact test (see Section 6.4.1).

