# 5.2 Baseline characteristics

A descriptive comparison of the randomised groups will be conducted on the baseline characteristics presented in the following table.

Baseline characteristic	Categories
City	Adelaide
	Melbourne
	Perth
	Sydney
Maternal age in years	-
Maternal ethnicity	Caucasian
	Aboriginal/Torres Strait Islander
	Maori/Pacific Islander
	African
	Middle Eastern
	Mediterranean
	East Asian
	South/South East Asian
	Other
Maternal school education - completion of secondary	Yes/No
school	
Maternal further education	No further study
	Certificate/diploma
	Degree
	Higher degree
Maternal smoking	Yes/No
Other smoking in the household	Yes/No
Pet dog(s)	Yes/No
Pet cat(s)	Yes/No

Version 1.0

PrEggNut Study Statistical Analysis Plan	Page 11
Pet chicken(s)	Yes/No
Parity	First born child
	Subsequent born child
Gestation at randomisation in weeks	-
Pre-pregnancy weight in kg	-
Current weight in kg	-
Maternal BMI in kg/m 	-
Maternal history of allergic disease	Yes/No
Paternal history of allergic disease	Yes/No
Sibling history of allergic disease	Yes
	No
	Not applicable
Maternal history of food allergy	Yes/No
Paternal history of food allergy	Yes/No
Sibling history of food allergy	Yes
	No
	Not applicable
Maternal peanut intake per week	-
Total household peanut intake per week	-
Maternal egg intake per week	-
Total household egg intake per week	-
Maternal egg specific-IgG4 levels	-
(Perth and Sydney women only)	
Maternal peanut specific-IgG4 levels	-
(Perth and Sydney women only)	
Infant sex	Female
	Male

Means and standard deviations, or medians and interquartile ranges will be reported for continuous variables. Frequencies and percentages will be reported for categorical variables. The clinical importance of any observed imbalances will be noted.

Version 1.0

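### The exploratory maternal IgG4 outcomes are not adjusted for the baseline maternal IgG4 already measured, which costs precision but does not bias the comparison

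*SAP*

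**What the plan says.** Section 5.2 includes "Maternal egg specific-IgG4 levels" and "Maternal peanut specific-IgG4 levels" among the baseline characteristics, for Perth and Sydney women only. The one use it gives them is descriptive: "A descriptive comparison of the randomised groups will be conducted on the baseline characteristics presented in the following table". It adds that the clinical importance of imbalances will be noted.

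Section 6.3.1 then defines "Continuous outcomes based on egg specific IgG4 levels (mgA/L) in maternal blood samples at 34-38 weeks gestation and 4 months postnatal age", and Section 6.3.2 defines "Continuous outcomes based on peanut specific IgG4 levels (mgA/L) in maternal blood samples at 34-38 weeks gestation and 4 months postnatal age", again for Perth and Sydney women only.

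Under Section 6.4.1, "the exploratory laboratory outcomes (Section 6.3) will be analysed using tobit regression models", on log-transformed concentrations, with the effect reported as a ratio of means. Section 6.4.2 adjusts for city and birth order and continues: "Adjustment will also be made for infant sex and maternal history of allergic disease". The reason given for these last two is their prognostic value for allergic disease in the infant. For each outcome, the adjusted analysis is the one from which conclusions are drawn. No separate covariate set is given for the laboratory outcomes.

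**The concern.** For a continuous laboratory measure, the same person's pre-treatment value is usually the most useful covariate available. Here it is collected and will be tabulated, but it is not in the model. The covariates that are in the model were chosen for infant allergic disease, and the SAP offers no argument that they predict maternal antibody levels.

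Two things follow. Stable differences between women that existed before randomisation stay in the error term and widen the interval for the ratio of means. If the groups differ by chance at baseline, Section 5.2 makes that visible, but the prespecified analysis does nothing about it. Adding the covariate after seeing an imbalance would have to be documented as a deviation or a post-hoc analysis under Section 1. These outcomes come from two of the four cities, so there are fewer women to absorb the loss.

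**Working it through.** **Plan's own figures.** The SAP gives no standard deviation, power or sample size for maternal IgG4. Its only sample size is for the primary outcome (Section 3.3): 16% versus 11.2%, 85% power, two-sided alpha 0.049, continuity correction. That reproduces as 961 per group, and 961 / 0.9 = 1067.8, rounded up to 1068. This point does not touch it.

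**Is the baseline value used anywhere in a model?**

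| Section | Maternal IgG4 at baseline |
|---|---|
| 5.2 | Listed, compared descriptively |
| 6.3.1, 6.3.2 | Only the later time points are outcomes |
| 6.4.1 | Model type and transformation only |
| 6.4.2 | Not in the covariate set |
| 6.4.3 | Subgroup analyses are for the primary outcome only |
| 6.4.5 | Laboratory outcomes analysed on complete outcome data; baseline not mentioned |

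It enters no model.

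**Linear benchmark.** Let r be the correlation between log baseline and log follow-up IgG4 (assumed; not in the SAP). Without censoring, adding the baseline multiplies the variance of the treatment effect by 1 − r² and the interval width by √(1 − r²). At r = 0.7, for example, 1 − 0.49 = 0.51 and √0.51 = 0.714.

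**Tobit check.** The planned model has a detection limit (0.07 mgA/L for IgG4), so the linear figures are only a guide. Tobit models were simulated with 400 women in total (an assumption), a true log-scale effect of 0.25, about 10% or 30% of baseline and follow-up values below the limit, and 400 replicates per setting. Treatment alone was compared with treatment plus the baseline, entered as the log value floored at the limit with a below-limit indicator. A further simulation also made 10% of baselines missing and added a missing-indicator. The entries are standard-error ratios, with baseline over without.

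| r | √(1 − r²) | 10% below limit | 30% below limit | With 10% baselines missing | Interval narrower by |
|---|---|---|---|---|---|
| 0.3 | 0.954 | 0.969 | 0.961 | about 0.95 | 3–5% |
| 0.5 | 0.866 | 0.857 | 0.909 | 0.88–0.92 | 8–14% |
| 0.7 | 0.714 | 0.711 | 0.764 | 0.73–0.76 | 24–29% |
| 0.8 | 0.600 | 0.632 | 0.646 | 0.67–0.68 | 32–37% |

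The last column is 1 minus the largest and smallest simulated ratio in the row. At r = 0.5, for example, 1 − 0.92 = 8% and 1 − 0.857 = 14%. As a sample-size equivalent, 1 / ratio² gives about 1.1, 1.2–1.4, 1.7–2.0 and 2.2–2.5 times the women.

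The simulated mean effects were 0.238 to 0.256 without the baseline and 0.238 to 0.255 with it, against the true 0.25, so neither model shows material bias. The few ratios slightly below the linear value are simulation noise: the relative error of a ratio is about r / √400, so at r = 0.5 it is 0.025 × 0.866 ≈ 0.02.

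**Chance imbalance.** If the groups differ by d in mean log baseline IgG4, the comparison without the baseline shifts by the follow-up-on-baseline slope times d. With equal spread at both times, that slope equals r.

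**The case against.** The strongest reply is that this is a preference about efficiency. Randomisation makes the comparison of follow-up IgG4 valid without the baseline, and the prespecified model is coherent. The outcomes are exploratory, and Section 6.4.5 already uses that status to justify simpler handling of missing data. A common covariate set is also simple and needs no rule for censored or missing baseline samples. All of this stands, and it limits the priority. It does not remove the point, because the covariate is already in hand and the SAP itself accepts adjustment for prognostic variables.

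The size is also open to challenge. No correlation is given, and it may differ between 34–38 weeks and 4 months postnatal. The planned model already contains other covariates, so the relevant r is the partial correlation given those, and the gain may be smaller than shown. At r = 0.3 it is slight.

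A reader might infer more than the document supports:
- **That the maternal IgG4 results would be biased.** They would not.
- **That a chance imbalance passes in full into the ratio of means.** It passes only in proportion to the slope.
- **That the linear figures apply as they stand**, such as a 40% narrower interval or 2.8 times the sample at r = 0.8. Simulation with censoring gives 32–37% and 2.2–2.5 times.
- **That including infant sex does harm.** One uninformative covariate costs almost nothing.
- **That the infant antibody outcomes share the problem.** Section 5.2 lists no infant antibody baseline.
- **That the SAP relies on IgG4 to verify the dietary contrast.** It assigns these outcomes no such role.

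**Conclusion.** The point holds as a loss of precision in two exploratory outcomes. Section 6.4.2 leaves out a baseline measurement that Section 5.2 shows is available, without giving a reason, and the model so specified decides the conclusions for those outcomes. The avoidable interval width runs from a few percent at r = 0.3 to about a third at r = 0.8, and part of any chance baseline imbalance stays uncorrected.

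This rests on the assumed range of r, on 10% to 30% of values lying below the limit, and on the baseline sample being drawn before the diets could affect IgG4. The SAP calls the sample baseline but does not give its timing. The primary and secondary clinical analyses are unaffected. Priority is low to moderate.

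**What to change.** In Section 6.4.2, for outcomes 6.3.1 and 6.3.2 only, add log baseline maternal IgG4 for the same allergen to the adjusted tobit model at both time points. State three rules with it:

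- Baseline values below 0.07 mgA/L are set to the limit, with a below-limit indicator.
- Women without a baseline sample are kept by a missing-indicator. Otherwise the covariate would drop women whom Section 4.3 includes because they gave a sample at the outcome time point. The indicator is acceptable here because missingness of a pre-randomisation measurement cannot depend on allocation.
- The place of baseline IgG4 in the removal sequence for non-convergence is given; removing it last is sensible.

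The cost is a short paragraph in the SAP and a few lines of code. The SAP already plans to report these baseline values, so no new data collection is implied. The change should be made before treatment codes are released to the trial statistician.

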### 6.4.3 Planned subgroup analyses

For the primary outcome only, analyses will be performed to test for evidence of effect modification by (1) birth order (first or subsequent born child to the mother), (2) baseline total household egg intake, (3) baseline total household peanut intake, and (4) socio-economic status, determined using the home post-code of the mother and the index of relative socio-economic advantage and disadvantage (www.abs.gov.au/websitedbs/censushome.nsf/ home/seifa). Effect modification by birth order will be assessed by including this subgroup variable as well as its interaction with treatment group into the log binomial regression model for the primary outcome (with the covariates detailed in Section 6.4.2 also included in the model). Effect modification by total household egg intake, total household peanut intake and socio-economic status will be assessed in a similar fashion in separate log binomial models, but with these variables treated as continuous rather than categorical in the analysis. To account for potential non-linear effects, two-term fractional polynomials will be fitted using the "mfpi" command in Stata v16 (or later) using default settings (7). For each potential effect modifier, the p-value for the interaction term with treatment group will be reported. Independent of the statistical significance of the interaction p-value, estimates of the treatment effect with 95% confidence intervals will be reported for each birth order subgroup or in treatment effect plots for total household egg intake, total household peanut intake and socio-economic status.

### 6.4.4 Methods for addressing outlying values

Outliers will be queried during data collection and the statistical analysis. Unless confirmed as a data entry error, outliers will not be excluded from any analyses.

#### Statistical Analysis Plan

Page 17

#### 6.4.5 Methods for handling missing data

Missing data will be summarised descriptively by treatment group for all baseline characteristics (Section 5.2), post-randomisation characteristics (Section 5.3), outcome variables (Sections 6.1 to 6.3), covariates for adjustment (Section 6.4.2) and covariates for subgroup analyses (Section 6.4.3). Composite binary outcomes (6.1.1, 6.2.3 and 6.2.4) will be treated as missing if any of the individual components of the outcome are missing, even if the composite can be derived from the observed components. Variables not ascertained due to infant death will not be treated as missing, as such data are not meaningful for analysis. Instead, these data will be treated as undefined and excluded from analyses (see Section 6.4.6).

To address missing data on the primary outcome and secondary clinical outcomes, multiple imputation performed under a missing at random assumption will be used to create 100 complete datasets for analysis, even if only a small percentage of data are missing. Use of 100 imputations ensures that the loss of power compared to full information maximum likelihood methods is minimal (8), which is important in the context of a confirmatory clinical trial. Imputation will be performed separately by treatment group using fully conditional specification, also known as chained equations. The conditional logistic imputation models for the incomplete outcomes will include covariates prespecified for adjustment (Section 6.4.2) and for conducting subgroup analyses (Section 6.4.3). Additional auxiliary variables associated with the incomplete outcomes will also be added to the imputation model as appropriate to improve the prediction of missing values and the plausibility of the missing at random assumption. For composite binary outcomes (6.1.1, 6.2.3 and 6.2.4), conditional logistic imputation models will be defined for each component and the composite outcome calculated following imputation.

For the primary outcome, the sensitivity of results to the missing at random assumption will be explored by considering missing not at random mechanisms. Using pattern mixture models, the odds of IgE mediated egg and/or peanut allergy will be assumed to be between half and twice as high in children with missing data compared to children with observed data. These differences will be applied to control group children only, treatment group children only and children in both treatment groups.

For the primary outcome and secondary clinical outcomes, a complete case analysis will also be performed on the unimputed data for comparison with imputed results. However, these analyses will not be used to inform conclusions about the effect of treatment.

Version 1.0

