## **3.5** Statistical interim analyses and stopping guidance

An independent statistician will conduct a single interim analysis of the primary outcome once 961 infants (50% of the planned sample size, accounting for loss to follow-up) have primary outcome data available. The analysis will be performed according to the statistical methods described in Section 6. An independent Data Monitoring Committee will review the results of this analysis and employ O'Brien-Fleming stopping criteria (1) to maintain the overall alpha for the primary outcome across interim and final analyses at 0.05. A two-sided p-value of less than 0.0031 at the interim analysis (symmetric stopping boundary of  $Z = \pm 2.96259$ ), indicating a large difference between treatment groups, will be taken to provide statistical evidence in support of early stopping. A p-value of 0.0490 ( $Z = \pm 1.96857$ ) will be used to indicate statistical significance at the final analysis.

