## 4.3 Analysis populations

For the primary outcome and secondary clinical outcomes (detailed in Sections 6.1 and 6.2), the planned analyses will be performed using an ITT approach. Excluding infant deaths occurring prior to outcome measurement (see Section 6.4.6 for more detail), the ITT population will include all randomised women-infant pairs, analysed as randomised, irrespective of eligibility or compliance with the protocol. For the primary outcome only, a sensitivity analysis will also be performed using a per-protocol approach. The per-protocol population will consist of all women-infant pairs that:

- Followed dietary consumption and breastfeeding recommendations (as described in Section 4.2);
- Did not report a protocol deviation (as described in Section 4.2);
- Provided data on the primary outcome at 12 months.

For exploratory laboratory outcomes (Section 6.3) collected in Perth and Sydney, the analysis population will consist of all women or infants that provided a blood sample at the relevant time point, analysed according to their randomised group.

Statistical Analysis Plan

Page 9

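### Section 6.4.5 treats an unperformed food challenge as a missing component even when a negative skin prick test has already settled the result as no allergy

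*SAP*

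**What the plan says.** - **Outcome (SAP 6.1.1, 6.2.3, 6.2.4).** Allergy to a food is a reaction to it together with sensitisation to it, and sensitisation is an SPT weal of 3 mm or more. The primary outcome is allergy to egg, peanut or both. An SPT-positive infant who is not challenged because of an earlier reaction counts as positive; "otherwise, the allergic reaction will be established according to an oral food challenge".
- **Missing composites (SAP 6.4.5).** Outcomes 6.1.1, 6.2.3 and 6.2.4 are "treated as missing if any of the individual components of the outcome are missing, even if the composite can be derived" from the observed components.
- **Imputation (SAP 6.4.5).** For these composites, "conditional logistic imputation models will be defined for each component and the composite outcome calculated following imputation".
- **Complete-case analysis (SAP 6.4.5).** For the primary and secondary clinical outcomes, "a complete case analysis will also be performed on the unimputed data for comparison with imputed results", but "these analyses will not be used to inform conclusions about the effect of treatment".
- **Per-protocol set (SAP 4.3).** One entry condition is "Provided data on the primary outcome at 12 months". The analysis is a sensitivity analysis.
- **Interim (SAP 3.5).** The look takes place "once 961 infants (50% of the planned sample size, accounting for loss to follow-up) have primary outcome data available", and the data are analysed by the methods of Section 6.
- **Missing-not-at-random analysis (SAP 6.4.5).** The odds of allergy in children with missing data are taken to be between half and twice those in children with observed data.

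The SAP does not state whether SPT-negative infants are challenged, or whether a challenge that was not needed counts as a missing component.

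**The concern.** Because the rule lists 6.2.3 and 6.2.4, it works within each food and not only across egg and peanut. Within a food, a negative SPT settles the answer whatever the challenge would have shown. The rule overrides exactly that deduction.

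The only unchallenged infants whose status Section 6.1.1 settles are SPT-positive infants with an earlier reaction. Its wording about SPT-positive infants who do not go on to challenge suggests that challenge follows a positive SPT. If so, an SPT-negative infant has no reaction result, and the literal rule makes that infant's outcome missing.

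The unimputed analyses would then be restricted largely to sensitised infants. Sensitisation is measured after randomisation and forms part of the outcome. The absolute risks would be far too high, and the relative risk would no longer estimate the planned effect.

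**Working it through.** **1. The plan's own figures.** Inputs from SAP 3.3: 16% v 11.2%, power 85%, two-sided alpha 0.049, continuity correction, 10% loss.

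- Uncorrected: n = [z(1−α/2)·√(2p̄(1−p̄)) + z(power)·√(p₁q₁ + p₂q₂)]² / d², with p̄ = 0.136 and d = 0.048. This gives 919.5, so 920.
- Corrected: (n/4)·[1 + √(1 + 4/(nd))]² = 960.7, so 961 per group.
- With 10% loss: 961/0.90 = 1067.8, so 1068 per group.
- Interim count: 961/(2 × 961) = 50%.

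All agree with the SAP. The missing-component rule does not change them.

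**2. What each within-food pattern determines.**

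| SPT | Challenge | Allergy by 6.1.1 | Literal 6.4.5, unimputed data |
|---|---|---|---|
| ≥3 mm | done | determined | kept |
| ≥3 mm | not done, earlier reaction | yes | kept (6.1.1 settles it) |
| ≥3 mm | not done, other reason | undetermined | missing |
| <3 mm | done | no | kept |
| <3 mm | not done | **no** | **missing** |
| not done | any | not derived from the two components | missing |

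The fifth row is the fault.

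**3. Size if only SPT-positive infants are challenged.** The SAP gives no SPT rates, so these are assumptions: egg SPT-positive e, peanut SPT-positive p, correlation r. All four components are then observed only in infants positive to both foods:

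P(both) = ep + r·√(e(1−e)p(1−p)), capped at p; P(neither) = 1 − (e + p − P(both)).

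| e | p | r | P(both) | P(neither) | All four observed, of 1922 |
|---|---|---|---|---|---|
| 0.20 | 0.10 | 0.5 | 0.08 | 0.78 | 154 |
| 0.25 | 0.10 | 0.5 | 0.09 | 0.74 | 173 |
| 0.30 | 0.12 | 0.6 | 0.125, capped at 0.12 | 0.70 | 231 |

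So 70-78% of infants are known negatives for both foods and would be labelled missing. About 8-12% would be kept.

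**4. Effect on the complete-case estimate.** Simplify to one test and one challenge, with 20-30% SPT-positive in the control group. Complete-case control risk = 0.16/0.20 = 80%, or 0.16/0.30 = 53%, instead of 16%.

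The relative risk then depends on how the diet acts:

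- Sensitisation unchanged: 0.112/0.20 = 56%, and 56/80 = 0.70.
- Sensitisation also cut by 30%, to 14%: 0.112/0.14 = 80%, and 80/80 = 1.00.

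Both are illustrations. They show that a real effect could disappear from the comparison.

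**5. The primary analysis.** Components are imputed and the composite is formed afterwards. For an SPT-negative infant, whatever reaction is imputed, the result for that food is still no. The imputed intention-to-treat estimate therefore keeps every result the SPT has settled.

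**6. Across the two foods.** If one food's result is missing, only a positive and/or composite can be derived. Assume a fraction m lacks one food's result completely at random, and the observed food identifies a share s of true positives. Keeping derivable results gives:

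risk = [p(1−m) + spm] / [(1−m) + spm], where p is now the true risk.

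For p = 0.16 and m = 10%, this is 16.4% (s = 0.3) to 17.3% (s = 0.9), against a true 16%. With s = 0.9 and m differing by arm, the relative risk moves from 0.70 to 0.1218/0.1625 = 0.75 (m = 10% treatment, 2% control) or 0.1138/0.1732 = 0.66 (2% treatment, 10% control). Under the same missingness, the SAP's rule leaves both risks and the relative risk unbiased.

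**The case against.** **The natural reading is harmless.** A challenge that was not indicated is more naturally not applicable than missing. The damaging reading also sits badly with the plan, which expects 961 infants with primary outcome data. Who is challenged may be set out in the protocol. This is a fair reason to doubt that the literal reading was intended. It does not remove the problem, because the sentence expressly overrides derivation and names the single-food outcomes.

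**Little weight rests on the affected analyses.** This stands, and it limits the severity. The complete-case analysis does not inform conclusions, and the per-protocol analysis is a sensitivity analysis.

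A reader might infer three stronger things that the SAP does not support:

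- *That the primary result is damaged.* It is not, because the composite is formed after component imputation.
- *That the rule wrongly discards an infant with proven egg allergy and no peanut result.* In unimputed data that exclusion is defensible. Only positives could be rescued, and keeping them selects on the outcome (step 6 of the working). The imputed analysis keeps these infants.
- *That the interim could never happen.* The 961 is only a trigger, and the interim analysis uses the Section 6 methods, including imputation. Linking the count to the rule in 6.4.5 is an inference; Section 3.5 does not define when data are available.

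**Conclusion.** The point holds within each food. As written, Section 6.4.5 sets to missing a result that a negative SPT has already determined. If SPT-negative infants are not challenged, most known negatives leave the complete-case and per-protocol analyses. They would also be counted as children with missing data in the missing-not-at-random analysis. How far that changes its results depends on whether the odds shift is applied to the composite or to the components, which the SAP does not say. The interim trigger may be affected, in timing only.

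The sizes (8-12% of infants kept; a complete-case control risk of 53-80% in the one-food simplification) rest on assumed SPT rates and on challenge being limited to SPT-positive infants. If every infant is challenged, the within-food fault largely disappears.

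Severity is minor to moderate: only secondary and sensitivity analyses, and possibly the interim count, are touched.

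**What to change.** Amend Section 6.4.5 along these lines:

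*If the SPT to a food is below 3 mm, allergy to that food is coded no, and an unperformed challenge is not applicable rather than a missing component. In unimputed data the egg and/or peanut composite is missing if either egg allergy or peanut allergy status is undetermined.*

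The second sentence keeps the existing rule across foods and gives it a stated scope. Then use this one definition of primary outcome data for the interim count in Section 3.5, the per-protocol condition in Section 4.3, and the complete-case and missing-not-at-random analyses in Section 6.4.5. Stating which infants are challenged, or citing where the protocol says so, would remove the remaining doubt.

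The cost is a few sentences of SAP text and a few lines of derivation code. No new data are needed, and the sample size and stopping boundaries do not change.
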